4.1 Inclusion Criteria

...

7. Screening NT-proBNP >600 ng/L and <8500 ng/L; in patients with permanent or persistent atrial fibrillation, screening NT-proBNP >600 ng/L and <8500 ng/L.

...

4.2. Exclusion Criteria

5. Has any of the following laboratory parameter assessments at screening:
 - a. Aspartate transaminase (AST) or alanine transaminase (ALT) levels $>2.0 \times$ the upper limit of normal (ULN).
 - b. Total bilirubin $>2 \times$ ULN. ~~Patients with elevated total bilirubin that is secondary to documented Gilbert's syndrome are eligible if total bilirubin $<2 \times$ ULN.~~
9. Is currently taking diflunisal; if previously on this agent, must have at least a ~~6 month~~**30-day** wash-out prior to dosing (Day 1).

Purpose: Added clarification for inclusion Criterion 4b.

The primary change occurs in Section 4.1, Inclusion Criteria

Revised text:

4. Patient meets one of the following criteria:
 - a. Tafamidis naïve; in addition to patients who have never taken tafamidis, those who have been on tafamidis for ≤ 30 days total and have not received any tafamidis in the 6 months prior to baseline will be considered tafamidis naïve and may qualify for the study.
 - b. Currently on tafamidis (for ≥ 6 months) and has demonstrated disease progression, as determined by the Investigator. (At the time of study entry, tafamidis treatment must be on-label use of commercial tafamidis **for the treatment of ATTR amyloidosis with cardiomyopathy at the approved dose in the country of use.**)

Purpose: Added clarification that use of doxycycline is permitted for short-term treatment of infection.

The primary change occurs in Section 5.3, Concomitant Medications and Procedures

Revised text:

Inotersen, doxycycline, ursodeoxycholic acid, taurooursodeoxycholic acid, and diflunisal are also prohibited during the study (see **exclusion Criterion 10 in Section 4.2**). **Doxycycline is permitted if being taken for short-term treatment of infection.**

Purpose: Added clarification that study personnel performing assessments related to the primary and secondary efficacy endpoints will not reference the results of any previous assessments.

The primary change occurs in Section 3.6, Blinding

Revised text:

In addition, the study personnel performing assessments related to the primary and secondary efficacy endpoints will ~~also be blinded to~~ ~~will not~~ reference the results of any previous assessments.

Purpose: Added clarification that TTR genotyping may be conducted at a central laboratory; or a local laboratory selected in consultation with the Medical Monitor. Added that diagnostic testing for inclusion criterion 2c/d may be conducted at a laboratory or diagnostic center selected by the site, in consultation with the Medical Monitor, in countries in which this test is not standard of care.

The primary change occurs in Section 6.1, Screening Assessments

Revised text:

If a genetic test result that shows the presence or absence of a TTR pathogenic mutation, which would be consistent with either wtATTR or hATTR, is not available at Screening for the assessment of eligibility (Section 4.1, inclusion Criterion 2a), genotyping may be conducted at a **central** laboratory. **Alternatively, a local laboratory may be selected by the site study center** in consultation with the Medical Monitor.

The study eligibility biopsies and technetium scintigraphy noted in inclusion Criterion 2 are intended to be historical, as part of the patient's clinical care and diagnosis, and are not performed as part of the study.

If a diagnostic result that confirms ATTR amyloidosis is not available at Screening for the assessment of eligibility (inclusion Criterion 2c/d), testing may be conducted at a laboratory or diagnostic center selected by the site, in consultation with the Medical Monitor, in countries in which this test is not standard of care.

APOLLO-B: A Phase 3, Randomized, Double-blind, Placebo-controlled Multicenter Study to Evaluate the Efficacy and Safety of Patisiran in Patients with Transthyretin Amyloidosis with Cardiomyopathy (ATTR Amyloidosis with Cardiomyopathy)

Short Title

APOLLO-B: A Study to Evaluate Patisiran in Patients with Transthyretin Amyloidosis with Cardiomyopathy (ATTR Amyloidosis with Cardiomyopathy)

Study Drug

Patisiran (ALN-TTR02)

Phase

Phase 3

Study Center(s)

The study will be conducted at approximately 65 clinical study centers worldwide.

Objectives and Endpoints

Objectives	Endpoints
Primary	
To evaluate the efficacy of patisiran compared with placebo treatment on functional capacity (6-minute walk test [6-MWT]) in patients with ATTR amyloidosis with cardiomyopathy	Change from baseline at Month 12 in 6-MWT
Secondary	
• Change from baseline at Month 12 in Kansas City Cardiomyopathy Questionnaire Overall Summary (KCCQ-OS) score• Composite endpoint of all-cause mortality, frequency of cardiovascular (CV)-related hospitalizations and change from baseline in 6-MWT over the 12-month double-blind period• Composite endpoint of all-cause mortality and frequency of all-cause hospitalizations over the 12-month double-blind period

Objectives	Endpoints
Exploratory	

To evaluate the efficacy of patisiran compared with placebo treatment on:
 
 • All-cause mortality and CV-related hospitalizations • Cardiac biomarkers and biomarker-based risk assessment • Manifestations of cardiac amyloid involvement 	
 • Composite endpoint of all-cause mortality and frequency of CV-related hospitalizations over the 12-month double-blind period • Change from baseline at Month 12 in: 
 ◦ N-terminal prohormone B-type natriuretic peptide (NT-proBNP) ◦ ATTR amyloidosis disease stage • Change from baseline at Month 12 in: 
 ◦ New York Heart Association (NYHA) Class ◦ Echocardiographic parameters ◦ Modified body mass index (mBMI) ◦ Cardiac magnetic resonance (CMR) parameters ◦ Technetium scintigraphy parameters ◦ Troponin I levels ◦ Norfolk QoL-DN
Pharmacodynamics (PD) and Pharmacokinetics (PK)	

 • To evaluate the PD effect of patisiran on transthyretin (TTR) reduction • To determine the plasma concentration of patisiran and 2 lipid excipients • To assess presence of anti-drug antibodies (ADA) 	
 • Change from baseline in serum TTR levels through Month 12 • Plasma PK exposure parameters (maximum plasma concentration at end of infusion [C_{max}], 30-minute post-infusion concentration [$C_{p(30min)}$], and pre-infusion concentration [C_{min}]) • Frequency and titer of ADA
Safety	

 • To evaluate the safety and tolerability of patisiran in patients with ATTR amyloidosis with cardiomyopathy 	
 • Frequency of adverse events (AEs)

Study Design

This is a Phase 3, randomized (1:1), double-blind, placebo-controlled, multicenter study to evaluate the efficacy and safety of patisiran in approximately 300 patients with ATTR amyloidosis (hereditary or wt) with cardiomyopathy. Approximately 20% of the study

population is anticipated to have hATTR and 80% wtATTR. In addition, at baseline, patients are either:

- Tafamidis naïve; or
- Currently on tafamidis (for ≥ 6 months), with disease progression in the opinion of the investigator. This group will be capped at 30% of total enrollment in the study.

The study consists of a screening period of up to 45 days, a 12-month, double-blind, placebo-controlled period, a 12-month, open-label extension period (during which all patients will receive patisiran), and a 28-day follow-up period.

After screening, during the 12-month double-blind period, eligible patients will be randomized to receive intravenous (IV) treatment every 3 weeks with either patisiran or placebo. Prior to receiving randomized, double-blind study drug (patisiran or placebo), to reduce the potential for an infusion related reaction (IRR) with patisiran, all patients will receive premedications at least 60 minutes before the start of their infusion. Study drug will be administered in the clinic as an approximately 80-minute IV infusion.

During the 12-month open-label extension period, all patients will receive treatment with open-label patisiran. Furthermore, patients who have received ≥ 3 consecutive doses of patisiran on this study at the clinical site with no evidence of IRRs or other drug-related adverse effects impacting safety and tolerability of the infusion may have patisiran administered at home during the open-label extension period, where applicable country and local regulations allow. Home administration of patisiran will be performed by a healthcare professional trained on the protocol and on administration of premedications and patisiran infusion.

To evaluate the efficacy of treatment with patisiran versus placebo in patients with ATTR amyloidosis with cardiomyopathy, the change from baseline in 6-MWT will be assessed at Month 12 (Weeks 52-53) as the primary endpoint; this assessment will also be performed at Month 6 (Weeks 25-26) and Month 9 (Weeks 37-38) in the double-blind period, and during the open-label extension period. The first secondary endpoint will assess change from baseline at Month 12 in the KCCQ-OS score.

Safety will be assessed throughout the double-blind and open-label extension periods of the study.

Number of Planned Patients

Approximately 300 patients are planned for enrollment in this study.

Diagnosis and Main Eligibility Criteria

This study will include adults age 18 (or age of legal consent, whichever is older) to 85 years of age, inclusive, with ATTR amyloidosis with cardiomyopathy (hereditary or wild-type [wt]) who, at baseline, are either: 1) tafamidis naïve (on tafamidis for ≤ 30 days and none within 6 months prior to baseline); or 2) currently on tafamidis (for ≥ 6 months) with disease progression in the opinion of the investigator.

Study Drug, Dose, and Mode of Administration

Patisiran is a ribonucleic acid (RNA) interference (RNAi) therapeutic consisting of a double-stranded small interfering RNA (siRNA) targeting TTR mRNA formulated in a lipid

nanoparticle (LNP). The patisiran drug product is a sterile formulation of ALN-18328 (siRNA targeting TTR) formulated as LNPs with lipid excipients (1,2-Dilinoleylxylo-N,N-dimethylpropylamine [DLin-MC3-DMA], 1,2-Distearoyl-sn-glycero-3-phosphocholine (DSPC), cholesterol, and PEG2000-C-DMG) in isotonic phosphate buffered saline.

All patients will receive premedications prior to study drug administration to reduce the risk of IRRs.

An IV infusion of double-blind study drug (patisiran 0.3 mg/kg or placebo) will be administered under the supervision of the site personnel once every 3 weeks \pm 3 days. Dosing is based on actual body weight. For patients weighing \geq 100 kg, the maximum recommended patisiran dose is 30 mg.

The last dose of double-blind study drug will be at Week 51 and the first dose of open-label patisiran will be 3 weeks later (at Week 54) and thereafter every 3 weeks (\pm 3 days) for the remainder of the study. Open-label patisiran will be administered per the schedule and dose as is described above for double-blind patisiran.

Reference Treatment, Dose, and Mode of Administration

The control drug for this study will be a placebo (normal saline 0.9% for IV administration). Control drug will be provided by a central supplier (or, if necessary, by a local supplier, with prior Sponsor approval).

Duration of Treatment and Study Participation

The treatment duration in this study is up to 24 months, inclusive of a 12-month, double-blind, treatment period, and a 12-month, open-label, treatment period. The estimated total time on study for each patient is up to 26.5 months, including up to 45 days of screening, up to 24 months of treatment, and a 28-day safety follow-up period.

Statistical Methods

The planned enrollment for this study is 300 patients. Randomization (1:1) will be stratified by: 1) baseline tafamidis (yes vs no); 2) genotype (hATTR vs wtATTR); and 3) NYHA Class I or II and age $<$ 75 years vs all other.

For the change from baseline at Month 12 in the 6-MWT, assuming a treatment difference of 33 meters between patisiran and placebo in the treatment-naïve group and 20 meters in patients with baseline tafamidis, the weighted average treatment difference between patisiran and placebo in the overall population is approximately 29 meters (standard deviation = 75 meters) assuming 70% are in the treatment-naïve group and 30% are in the baseline tafamidis group. A sample size of 300 patients provides $>90\%$ power for a 2-sided test to detect a treatment difference at a 2-sided alpha = 0.05. Additional patients may be enrolled based on a recommendation to increase the sample size in the interim assessment.

The primary endpoint, change from baseline at Month 12 in the 6-MWT, will be analyzed using a mixed-effects model repeated measures (MMRM) approach. The outcome variable is change from baseline in the 6-MWT. The model will include the baseline value as a covariate, treatment, visit, the treatment-by-visit interaction, baseline tafamidis (yes vs no), genotype (hATTR vs wtATTR), and age (<75 vs ≥ 75 years) as fixed factors, and patient as a random

effect. The primary comparison is the contrast (difference in least squares [LS] means) between the patisiran and placebo groups at Month 12.

To control the overall Type I error rate, secondary endpoints will be tested in a prespecified hierarchical order.

For patients who are tafamidis treatment-naïve at baseline and start tafamidis during the double-blind period, the primary analysis of the primary endpoint will censor data collected after the initiation of tafamidis treatment post-randomization.

Safety data will be summarized descriptively.

Figure 1: Study Design

[figure not shown]

Table 1: Schedule of Assessments – Double-blind Period (Screening to Month 12 Efficacy Assessments)

Table 1: Schedule of Assessments – Double-blind Period (Screening to Month 12 Efficacy Assessments)

Table 1: Schedule of Assessments – Double-blind Period (Screening to Month 12 Efficacy Assessments)

Abbreviations: AE=adverse event; ADA=antidrug antibodies; Con Meds=concomitant medications; CMR=cardiac magnetic resonance; D=day; Disc=discontinuation; ECG=electrocardiogram; FSH=follicle-stimulating hormone; KCCQ=Kansas City Cardiomyopathy Questionnaire; M=month;

mBMI=modified body mass index; 6-MWT=6-minute walk test; NA=not applicable; NT-proBNP=N-terminal prohormone B-type natriuretic peptide; NYHA=New York Heart Association; PK=pharmacokinetics; PND=Polyneuropathy Disability; QoL-DN=Quality of Life-Diabetic Neuropathy; TTR=transthyretin; V=visits.

^a This efficacy visit is conducted 7 to 14 days after the prior visit.

^b This Modified Month 12 Efficacy Visit is to be performed at Month 12 for patients who discontinued treatment early (ie, prior to Month 12), and choose to remain in the study. All patients who discontinue from study drug during the double-blind period will be encouraged to remain on the study and complete assessments through Month 12 (excluding PK assessments), including this Modified Month 12 Efficacy Visit. Such patients will also receive assessments at the Early Treatment Discontinuation Visit (7 to 14 days after their last dose of study drug); and the safety follow-up visit (28 days after the last dose of study drug) ([Table 2](#)), as described in Section 4.3.1.

^c See Section 5.3.1; patients who are tafamidis-naïve at baseline may opt to begin tafamidis treatment (ie, “tafamidis drop-in”) during the double-blind period. In all cases, the Pre-tafamidis Drop-in Visit should occur prior to starting concomitant tafamidis; where possible, this visit should occur between 1-2 weeks after the last dose of double-blind study drug (ie, 7 to 14 days post dose). Thereafter, the patient will continue with all assessments per the Schedule of Assessments, including the Month 12 Efficacy Visit. At the time of tafamidis drop-in, the reason for starting tafamidis will be recorded in the CRF.

^d As described in Section 6.2.1, to avoid a potential training effect resulting from repeated assessments of the 6-MWT within a short period of time, only one 6-MWT assessment should be performed within each of the following time periods: Day 2 to Day 214 (includes the scheduled Weeks 25-26 assessment); Day 215 to Day 319 (includes the scheduled Weeks 37-38 assessment); and Day 320 to Day 372 (includes the scheduled Weeks 52-53 assessment). Within a given time period, the 6-MWT assessment should be performed at whichever visit occurs first (scheduled assessment, Pre-tafamidis Drop-in Visit, or Early Treatment Discontinuation Visit [[Table 2](#)]); no additional 6-MWT assessments should be made in that time period. In later time periods, the 6-MWT should be assessed as scheduled.

^e Serum creatinine only.

Table 2: Schedule of Assessments – Open-label Extension Period (Through Month 24), Early Treatment Discontinuation Visit, and Follow-up

Study Day ±Visit Window	For Details see Section	Open-label Extension Period																Early Treatment Disc Visit ^b	Follow-up														
		D379±3	D400±3	D421±3	D442±3	D463±3	D484±3	D505±3	D526±3	D547±3	79-80	D554-D561 ^a	81	D568±3	84	D589±3	87	D610±3	90	D631±3	91-92	D638-D645 ^a	93	D652±3	96	D673±3	99	D694±3	102	D715±3	105	D736±3	106-107
Study Week		54	57	60	63	66	69	72	75	78	79-80	81	84	87	90	91-92	93	96	99	102	105	106-107	109	D764±10	NA	7-14 Days after Last Dose	109	D764±10	Follow-up				
Efficacy Assessments																																	
6-MWT	6.2.1										X														X	X							
KCCQ	6.2.2											X													X	X							
mbMI	6.2.4							X																	X								
Cardiac Biomarker Samples	6.2.5.1					X					X														X	X							
ATTR amyloidosis disease stage	6.2.5.2																								X								
NYHA Class	6.2.5.3										X														X								
Echocardiogram	6.2.5.4											X													X								
CMR, technetium (select sites only)	6.2.5.6, 6.2.5.5											X													X								
Norfolk QoL-DN	6.2.6																								X								
Pharmacodynamic Assessments																																	
TTR Protein	6.3						X					X													X	X	X						
Exploratory Biomarkers (plasma, serum)	6.6						X					X													X								
Safety Assessments																																	
Vital Signs	6.5.1	X	X	X	X	X	X	X	X	X	X	X	X	X	X	X	X	X	X	X	X	X	X	X	X	X	X	X					
Weight	6.5.2	X	X	X	X	X	X	X	X	X	X	X	X	X	X	X	X	X	X	X	X	X	X	X	X	X	X	X					
Physical Exam (symptom-directed)	6.5.3	X	X	X	X	X	X	X	X	X	X	X	X	X	X	X	X	X	X	X	X	X	X	X	X	X	X	X					
Single 12-lead ECG	6.5.4						X				X						X							X		X							

Table 2: Schedule of Assessments – Open-label Extension Period (Through Month 24), Early Treatment Discontinuation Visit, and Follow-up

Study Day ±Visit Window	For Details see Section	Open-label Extension Period																		Early Treatment Disc Visit ^b	Follow-up															
		D379±3	D400±3	D421±3	D442±3	D463±3	D484±3	D505±3	D526±3	D547±3	79-80	D554-D561 ^a	D568±3	D589±3	87	D610±3	D631±3	90	91-92	D638-D645 ^a	93	D652±3	96	D673±3	99	D694±3	102	D715±3	105	D736±3	106-107	D743-D750 ^a	EOS			
Study Week		54	57	60	63	66	69	72	75	78	79-80	D554-D561 ^a	81	D568±3	84	D589±3	87	D610±3	90	91-92	D638-D645 ^a	93	D652±3	96	D673±3	99	D694±3	102	D715±3	105	D736±3	106-107	D743-D750 ^a	EOS	7-14 Days after Last Dose	
Serum Chemistry, Liver Function Tests	6.5.5							X																									X	X		
Hematology	6.5.5							X																									X	X		
Pregnancy Test	Table 3, 6.5.5.2			X			X						X																		X	X	X			
Review/Record Hospitalization, Urgent Care Visits, and Procedures																																				
Review/Record AEs, Con Meds	6.5.7, 5.3																																			
Vital Status Check	6.5.6	X	X	X	X	X	X	X	X	X	X	X	X	X	X	X	X	X	X	X	X	X	X	X	X	X	X	X	X	X	X	X				
Pharmacokinetic Assessments																																				
Plasma PK	6.4																																	X		
Drug Administration																																				
Premedication, Study Drug	5.2.1, 5.2.3	X	X	X	X	X	X	X	X	X	X	X	X	X	X	X	X	X	X	X	X	X	X	X	X	X	X	X	X	X	X					

Abbreviations: AE=adverse event; ADA=antidrug antibodies; Con Meds=concomitant medications; CMR=cardiac magnetic resonance; D=day; Disc=discontinuation; ECG=electrocardiogram; EOS=End of Study (visit); KCCQ=Kansas City Cardiomyopathy Questionnaire; mBMI=modified body mass index; 6-MWT=6-minute walk test; NA=not applicable; NT-proBNP=N-terminal prohormone B-type natriuretic peptide; NYHA>New York Heart Association; PK=pharmacokinetics; QoL-DN=Quality of Life-Diabetic Neuropathy; TTR=transthyretin; V=visits.

^a This efficacy visit is conducted 7 to 14 days after the prior visit.

^b Patients who discontinue early from study drug will be asked to complete the Early Treatment Discontinuation Visit (7-14 days after their last dose) and the safety follow-up visit, 28 days after the last dose of study drug. In addition, patients discontinuing early from study drug during the double-blind period will be encouraged to remain on the

study and complete assessments through Month 12 and complete the Modified Month 12 Efficacy Visit (see [Table 1](#)); they will also be asked to complete an Early Treatment Discontinuation Visit (7-14 days after their last dose) and the safety follow-up visit, 28 days after the last dose of study drug as described in Section [4.3.1](#).

^c Serum creatinine only.

TABLE OF CONTENTS

SPONSOR PROTOCOL APPROVAL	2
INVESTIGATOR'S AGREEMENT	3
PROTOCOL SYNOPSIS	4
TABLE OF CONTENTS.....	17
LIST OF TABLES	21
LIST OF FIGURES	21
LIST OF ABBREVIATIONS AND DEFINITIONS OF TERMS.....	22
1. INTRODUCTION	25
1.1. Disease Overview	25
1.2. Current Treatments	26
1.3. Patisiran Clinical Development	27
1.3.1. The Phase 3 APOLLO Study.....	28
1.3.1.1. Cardiac Results and Cardiac Subpopulation Data from APOLLO	28
1.3.2. Phase 3, Open-label Extension Study.....	29
1.4. Study Design Rationale	29
1.5. Dose Rationale.....	30
1.6. Benefit-risk Assessment	30
2. OBJECTIVES AND ENDPOINTS	32
3. INVESTIGATIONAL PLAN.....	33

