3.5. Method of Assigning Patients to Treatment Groups

Using the interactive response system (IRS), patients will be randomized 1:1 to the patisiran or placebo arm. Randomization will be stratified by:

1. Baseline tafamidis (yes vs no)
2. Genotype (hATTR vs wtATTR amyloidosis with cardiomyopathy)
3. NYHA Class I or II **and** age < 75 years vs all other

Each patient will be uniquely identified in the study by a combination of the site number and patient identification number. Upon signing the informed consent form (ICF), the patient will be assigned a patient identification number by the IRS. The Investigator or his/her designee will contact the IRS to randomize the patient after confirming that the patient fulfills all the inclusion criteria and none of the exclusion criteria.

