4. SELECTION AND WITHDRAWAL OF PATIENTS

4.1. Inclusion Criteria

Patients are eligible to be included in the study if all the following criteria apply:

Age and Sex

1. Age 18 (or age of legal consent, whichever is older) to 85 years, inclusive.

Patient and Disease Characteristics

2. Documented diagnosis of ATTR amyloidosis with cardiomyopathy, classified as either hATTR amyloidosis with cardiomyopathy or wtATTR amyloidosis with cardiomyopathy:

Hereditary ATTR amyloidosis with cardiomyopathy diagnosed based on meeting all of the following criteria:

- a. TTR pathogenic mutation consistent with hATTR.
- b. Evidence of cardiac involvement by echocardiography with an end-diastolic interventricular septal wall thickness >12 mm (based on central echocardiogram reading at screening).
- c. Amyloid deposits in cardiac or noncardiac tissue (eg, fat pad aspirate, salivary gland, median nerve connective sheath) confirmed by Congo Red (or equivalent) staining **OR** technetium (^{99m}Tc) scintigraphy (^{99m}Tc-3,3-diphosphono-1,2-propanodicarboxylic acid [DPD-Tc], ^{99m}Tc-pyrophosphate [PYP-Tc], or ^{99m}Tc-hydroxymethylene diphosphonate [HMDP]) with Grade 2 or 3 cardiac uptake, if monoclonal gammopathy of undetermined significance (MGUS) has been excluded.
- d. If MGUS, confirm TTR protein in tissue with immunohistochemistry (IHC) or mass spectrometry.

Wild-type ATTR amyloidosis with cardiomyopathy diagnosed based on meeting all of the following criteria:

- a. Absence of pathogenic TTR mutation.
- b. Evidence of cardiac involvement by echocardiography with an end-diastolic interventricular septal wall thickness >12mm (based on central echocardiogram reading at screening).
- c. Amyloid deposits in cardiac tissue with TTR precursor identification by IHC, mass spectrometry, **OR** technetium (^{99m}Tc) scintigraphy (^{99m}Tc-3,3-diphosphono-1,2-propanodicarboxylic acid [DPD-Tc], ^{99m}Tc-pyrophosphate [PYP-Tc] or ^{99m}Tc-hydroxymethylene diphosphonate [HMDP]) with Grade 2 or 3 cardiac uptake, if MGUS has been excluded.
- d. If MGUS, confirm TTR protein in cardiac tissue with IHC or mass spectrometry

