6.1. Screening Assessments

An ICF that has been approved by the appropriate Institutional Review Board (IRB)/Independent Ethics Committee (IEC) must be signed by the patient or legal guardian before the Screening procedures are initiated. All patients or their legal guardians will be given a copy of the signed and dated ICF. In addition, a medical records release form will be required of all patients for the purpose of obtaining vital status information from the patient's physician or from death registries.

See the Schedule of Assessments ([Table 1](#)) for a list of Screening visit assessments.

Patients will be screened to ensure that they meet all the inclusion criteria and none of the exclusion criteria. Rescreening (once) of patients is permitted with consultation of the Medical Monitor (see Section [6.1.2](#)).

Patient demographic data and medical history/disease history will be obtained, including completion of ophthalmologic history in the eCRF. Any changes to medical history occurring between the screening assessment and Day 1 will be updated prior to study drug administration.

If a genetic test result that shows the presence or absence of a TTR pathogenic mutation, which would be consistent with either wtATTR or hATTR, is not available at Screening for the assessment of eligibility (Section [4.1](#), inclusion criterion 2a), genotyping may be conducted at a laboratory selected by the site in consultation with the Medical Monitor.

The study eligibility biopsies and technetium scintigraphy noted in inclusion Criterion 2 are intended to be historical, as part of the patient's clinical care and diagnosis, and are not performed as part of the study.

An echocardiogram will be performed at screening Visit 1 and results confirmed centrally to assess study eligibility, as indicated in the Schedule of Assessments ([Table 1](#)).

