7.2.5.1. Primary Endpoint

The primary endpoint, change from baseline at Month 12 in the 6-MWT, will be analyzed using a mixed-effects model repeated measures (MMRM) approach. The outcome variable is change

from baseline in the 6-MWT. The model will include the baseline value as a covariate, treatment, visit, the treatment-by-visit interaction, baseline tafamidis (yes vs no), genotype (hATTR vs wtATTR), and age (<75 vs \geq 75 years) as fixed factors, and patient as a random effect. The primary comparison is the contrast (difference in least squares [LS] means) between the patisiran and placebo groups at Month 12.

Sensitivity analyses will be detailed in the SAP.

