7.2.5.2. Secondary Endpoints

Secondary endpoints are described in Section 2.

KCCQ-OS will be analyzed using a similar MMRM model as used for the primary endpoint.

The composite endpoint of all-cause mortality, frequency of CV-related hospitalizations and change from baseline in 6-MWT will be analyzed using a generalized rank-based win ratio method, which makes pairwise comparisons (for all possible patisiran/placebo patient pairs) of the 3 components in the hierarchical order specified above. The point estimate for the win ratio is defined as the total number of better outcomes divided by the total number of worse outcomes in the patisiran group. The detailed algorithm for assessment of this endpoint will be provided in the SAP.

The composite endpoint of all-cause mortality and all-cause hospitalizations will be analyzed using an Andersen-Gill model stratified by baseline tafamidis (yes vs no), including treatment, genotype (hATTR vs wtATTR), NYHA Class (I/II vs III), and age (<75 vs \geq 75 years) as covariates.

Patients who undergo a heart transplantation and/or ventricular assist device placement after randomization will be handled in the same manner as death in the primary analyses of mortality related endpoints.

To control the overall Type I error rate, secondary endpoints will be tested in a prespecified hierarchical order.

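### Age in years is collected, but the primary 6-MWT model and the Andersen-Gill model use only a cut at 75; adding continuous age would be a small, nearly free gain in precision

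*Protocol*

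**What the plan says.** All model text cited here is from the Amendment 1 protocol.

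- **Primary endpoint.** The synopsis (Statistical Methods) and Section 7.2.5.1 describe an MMRM with the baseline value as a covariate and a list of fixed factors that ends "baseline tafamidis (yes vs no), genotype (hATTR vs wtATTR), and age (<75 vs" 75 or older). There is no age term in years.
- **KCCQ-OS.** Section 7.2.5.2: "KCCQ-OS will be analyzed using a similar MMRM model as used for the primary endpoint". The age coding is not restated, so the two-level form is an inference, though a direct one.
- **Death and all-cause hospitalization.** Section 7.2.5.2 specifies an Andersen-Gill model stratified by baseline tafamidis, "including treatment, genotype (hATTR vs wtATTR), NYHA Class (I/II vs III), and age (<75 vs" 75 or older) as covariates.
- **Win-ratio composite.** Section 7.2.5.2 describes pairwise comparisons with no covariates, so age does not enter.
- **Randomisation.** In Section 3.5 the third stratum joins NYHA class I or II with "age < 75 years vs all other". Age at 75 is not a stratum by itself.
- **Availability of age.** Section 4.1 sets eligibility at "Age 18 (or age of legal consent, whichever is older) to 85 years, inclusive", and Section 6.1 states "Patient demographic data and medical history/disease history will be obtained".

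The original protocol of April 2019 has the same cut. The Amendment 2 summary of changes lists no change to the age term, but the full Amendment 2 text is in the part of the document not shown.

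**The concern.** The sponsor treats age as prognostic: it helps define a randomisation stratum and appears in the stated regression models. A single step at 75 then treats everyone below 75 as alike and puts a jump between patients of 74 and 76. The cut probably falls where many patients are. About 80% of the population is expected to have wild-type disease (Section 3.1), which Section 1.1 describes as typical after 70, and the upper age limit is 85. The baseline 6-MWT is described as a continuous covariate in the Amendment 1 rationale, and no reason is given for treating age differently.

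Any age effect that the step does not capture stays in the residual. What is at stake is precision: a slightly wider confidence interval for the Month 12 6-MWT contrast and, by the same reasoning, for the KCCQ-OS contrast and the recurrent-event model. The protocol names the covariates and their coding, so this is a choice already made and not a detail left to the SAP.

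**Working it through.** **Inputs from the protocol** (Sections 3.5 and 7.1): difference 33 m in tafamidis-naïve patients and 20 m in those on tafamidis, weights 70% and 30%, overall difference about 29 m, SD 75 m, 300 patients allocated 1:1, two-sided alpha 0.05, power stated as above 90%.

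**Inputs not in the protocol, taken as assumptions:** age roughly normal; its effect on the Month 12 change linear; share *p* of patients on one side of 75 from 50% to 20%; partial correlation *r* of age with the outcome, given the other covariates, of 0.1, 0.2 or 0.3.

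**Step 1: reproduce the stated power.** Weighted difference = 0.7 × 33 + 0.3 × 20 = 29.1 m, which matches about 29 m. Standard error = 75 × √(2/150) = 8.66 m. Noncentrality = 29/8.66 = 3.35. With 298 degrees of freedom the noncentral t gives 91.6%; the normal approximation gives 91.8%. The stated figure is correct.

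**Step 2: what one cut keeps.** For a normal covariate with a linear effect, the share of its explained variance kept by a cut at quantile *p* is k = φ(z_p)² / [p(1 − p)].

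| Split at 75 | k kept | Lost |
|---|---|---|
| 50/50 | 0.637 | 36% |
| 40/60 | 0.622 | 38% |
| 30/70 | 0.576 | 42% |
| 25/75 | 0.539 | 46% |
| 20/80 | 0.490 | 51% |

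Two checks by simulation. With age truncated at 85 (mean parameter 70 to 78, SD 5 to 10), the loss is 33% to 57%, and 33% to 49% when at least about 20% of patients lie on each side. With genotype and baseline 6-MWT also in the model, the loss is 37% to 46%.

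**Step 3: what that means for the trial.** Take 75 m as the residual SD with the two-level factor in the model. With age in years, the residual variance is multiplied by (1 − r²)/(1 − k r²). The equivalent number of patients is 300 × (1/ratio − 1).

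| r | Variance ratio, k = 0.637 to 0.490 | SD (m) | Patients of 300 | Power (t) |
|---|---|---|---|---|
| 0.1 | 0.996 to 0.995 | 74.9 to 74.8 | 1.1 to 1.5 | 91.7% |
| 0.2 | 0.985 to 0.979 | 74.4 to 74.2 | 4.5 to 6.4 | 92.0% to 92.1% |
| 0.3 | 0.965 to 0.952 | 73.7 to 73.2 | 10.8 to 15.1 | 92.5% to 92.8% |

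Example for r = 0.2 at a 50/50 split: (1 − 0.04)/(1 − 0.637 × 0.04) = 0.96/0.9745 = 0.985; SD = 75 × √0.985 = 74.4 m; 300 × (1/0.985 − 1) is about 4.5.

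These figures are for the 6-MWT only. No corresponding calculation was made for KCCQ-OS or the Andersen-Gill model.

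**The case against.** The strongest case against is that this is a preference and not a defect. A prespecified two-level covariate contradicts nothing in the protocol, biases nothing and leaves the type I error intact. The documents give neither an age distribution nor a correlation of age with outcome, and age acts only after baseline 6-MWT, genotype and tafamidis are in the model. At r = 0.1 the gain is about one patient. All of that stands, and it limits the weight of the point.

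The link to the randomisation also has force. The third stratum is built from NYHA class and age at 75. Amendment 1 removed NYHA from the MMRM, for parsimony and because it correlates with baseline 6-MWT. The 75-year factor is therefore the only component of that stratum left in the model. Replacing it with continuous age would move the model further from the randomisation. This argues for adding age in years, not for substituting it.

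Three stronger readings are tempting and are not supported:

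- **That a third to a half of the trial's information is lost.** The 36% to 51% is a share of what age explains, which may itself be small.
- **That every planned efficacy analysis is affected.** The win ratio has no age term, and the KCCQ-OS coding is only implied.
- **That the cut undermines the missing-at-random assumption.** Nothing in the document links age on either side of 75 to dropout, and missing-data handling is left to the SAP.

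The age range of 18 to 85 also overstates the practical spread. In a largely wild-type population few patients will be far below 70.

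**Conclusion.** The point holds as a minor efficiency improvement. The primary MMRM and the Andersen-Gill model use age only as below 75 versus 75 or older, and the KCCQ-OS model does so by inference, although exact age is held for every patient. Under a roughly normal age and a linear effect, the cut loses 36% to 51% of what age explains for splits between 50/50 and 20/80. Depending on the assumed correlation, the benefit of restoring it lies between about 0.1 and 1.2 power points.

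No result would be invalid if the plan stayed as it is. The conclusion also rests on Amendment 1 text: the Amendment 2 summary is silent on the age term, but the current model wording should be checked. This is worth doing if the models are being edited before unblinding; it is not a reason to hold up the trial.

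**What to change.** Before unblinding, add baseline age in years as a continuous covariate to the 6-MWT MMRM, the KCCQ-OS MMRM and the Andersen-Gill model. Keep the two-level factor at 75 beside it, or use the actual NYHA-and-age randomisation stratum in its place, so that each model stays tied to the randomisation. State the KCCQ-OS covariates explicitly instead of by reference. The 75-year cut can still serve for subgroup displays.

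The change is a line in the synopsis, in Sections 7.2.5.1 and 7.2.5.2, and in the SAP. It needs no new data and costs one degree of freedom per model. The added term assumes a linear age effect, but keeping the factor leaves room for a step at 75.
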